Results: Of the 99 records examined, 46 (46.5%) had the diagnosis of PTSD. Most of the Veterans were male (94.9%), with an average age of 45.3 years and majority were Caucasian (78.8%); approximately half (52.5% were single/never married. Of those with PTSD, 10 (21.5%) were referred to trauma focused treatment: of those 4 were referred to CPT, 1 was referred to Prolonged Exposure (PE), and the rest received unspecified trauma-focused therapy. Of those who received trauma-focused treatment, 4/5 (80%) completed 12 sessions. Retention at 3 months was **significantly different between groups**: of those referred to trauma focused therapy 10/10 (100%) were retained in treatment compared to 11/36 (30.5%) (p<.05) of those without referral to trauma focused therapy (See Fig 1). As a comparator, among those without PTSD (n=53) 28 were retained in treatment (52.8%). While PCL scores are not available in all cases, the n=5 who participated in the EBP had PCL scores documented in the record. *The average PCL score= 61.4 (range 53-68) at the beginning of therapy was significantly reduced to PCL= 29.2 (range 10-48) (p<.05) at the end of the 12-session intervention.* (See Fig 2)]

These studies demonstrate our group's extensive experience in the methodology proposed and our ability to recruit and safely and effectively conduct pharmacologic studies in Veterans with PTSD and comorbid substance use disorders. Further, it demonstrates our experience in conducting studies using standardized psychotherapy, notably CPT in individuals with comorbid disorders and in conjunction with pharmacotherapy.

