6. RESEARCH PLAN

Research design and methods

Overview: We propose to conduct a randomized, controlled trial with 160 (assuming a 30% drop out rate, for 120 participants) Veterans and civilians diagnosed with PTSD and comorbid OUD. This study will use *open*

randomization to 2 groups: (a) buprenorphine + CPT vs. (b) *buprenorphine + IDC*. All subjects will be maintained on buprenorphine and the standard clinical treatment. Participants will be recruited primarily through the clinical facilities at the VA and from other collaborators.

The Bedford VAMC has been added as an additional enrollment site for this study. The principal investigator for the Bedford site is [name] and the study will be overseen by the Bedford VA IRB has gained local IRB approval.

Experimental subjects: Veterans and civilians (n=160) aged 18- 65 years old, with a current diagnosis of PTSD and opioid use disorder (OUD) will be enrolled at 2 sites (VA Connecticut Healthcare System, Bedford VAMC) for a study with 12-weeks of active treatment. Participants will be recruited from four main sources: 1) from the PTSD clinic patients at the local VAs , 2) from the group of Veterans entering treatment for opioid use disorders at the local VA Substance Abuse Treatment Programs and 3) advertisement (flyers, posters, Craigslist) 4. Community clinics. Under a HIPAA waiver, IRB-approved letters of invitation can be mailed to prospective participants with a past diagnosis of OUD or PTSD who otherwise might meet eligibility criteria. Outreach will also be conducted at local Veteran Centers, where staff from both VAs consult. The PTSD staff has also been involved in outreach to the community for returning OIF/OEF Veterans. Each participant will be carefully screened and assessed using the following inclusion and exclusion criteria:

Inclusion Criteria:

- 1) Male and female Veterans and civilians between the ages of 18-70 years old.
- 2) Current diagnosis of PTSD as determined by an independent evaluator assessment using CAPS-5.
- 3) Opioid Use Disorder diagnosed by Mini International Neuropsychiatric Interview for DSM-5 (MINI). To meet entry criteria for buprenorphine treatment, will also have documented prior treatment for opioid use disorder, history of opioid withdrawal or signs of opiate withdrawal as evidenced by a Clinical Opiate Withdrawal Scale (COWS) score of 7 or greater, and a positive urine toxicology for opioids.

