- 4) For women, negative pregnancy test and use of acceptable method of contraception.

Please note, because of the high incidence of depression that co-occurs with PTSD, those individuals with comorbid depressive disorders will be allowed into the study. This is in keeping with the purpose of this study to evaluate the effectiveness of a CPT in a “real world” clinical population. It also is anticipated that a significant proportion of Veterans and civilians will likely be treated with concurrent antidepressant pharmacotherapy [and/or with other medications (eg. prazosin).] However, again this enhances the “real world” application of treatments within the VA system, and secondly it is common to allow antidepressant medication in psychotherapy trials and still be able to show benefit with CPT.[37] For those who are already prescribed antidepressant medication, they will be continued on their current pharmacologic treatment Please note that since not all subjects will be on psychotropic medications, randomization will be stratified by presence of concurrent medications-a strategy we have used successfully in other comorbidity studies with PTSD[71]

Exclusion Criteria:

- 1) Females who are pregnant or lactating.
- 2) Veterans and civilians with a current unstable medical condition such as neurological, cardiovascular, endocrine, renal, liver, or thyroid pathology (e.g. abnormal BUN and creatinine, and unmanaged hypertension with BP > 200/120) which in the opinion of the physician would preclude the patient from fully cooperating or be of potential harm during the course of the study.
- 3) Veterans and civilians who meet current criteria for the following diagnoses (schizophrenia and schizophrenia spectrum and psychotic disorders) as determined by the MINI.
- 4) Veterans and civilians who have significant current suicidal or homicidal risks necessitating a higher level of care.
- 5) Those with known allergy or intolerance to buprenorphine.

Methods:

Overview: This study is a 14-week, RCT with open-label randomization to 2 groups (described in detail below): (a) buprenorphine (BUP) + CPT vs. (b) BUP + IDC. This study will be conducted in 3 Phases: Phase I:

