makes it highly compatible with a pharmacologic intervention. Our group has extensive experience with MM in a comorbid group of patients.

Medication Compliance: We employ a number of strategies to ensure maximum compliance with the medication regimen. All medications will be dispensed in clearly labeled prescription vials. Before each visit each patient will receive a reminder phone call about his/her appointment and is also reminded to return the bottle with the study medication regardless of whether any medication is left over. At the beginning of each study visit the left-over medication will be counted, and the patient will be prompted to report any doubling of dose or missing days of study medication. If the visit is completed via video, the patient will be asked to count the medication "in front" of the research staff member. If the visit is completed by telephone (without a video option), the patient will be asked to count the remaining study medication and report this to the staff member conducting the visit; accountability will be conducted during the monthly in-person visits. Since BUP/NXL is a controlled substance, study staff will instruct the participant on how to properly dispose of any leftover medication, in a manner that is compliant with VA policy (e.g. take back envelopes, flushing down the sink/toilet, or by placing in CS waste disposal bins while being observed by VA staff). The session will also provide an opportunity for subjects to review critical issues and problem areas, the subjects' involvement in any ancillary treatments, and other clinically significant events. Other formal treatment concurrent with their study treatment (including self-help meetings) will be monitored.

All medications (buprenorphine) will be prescribed by the study physicians or individuals' current physician. Participants will be seen weekly by research staff for the first four weeks then biweekly for 1 month, and then monthly. There will be close monitoring for psychiatric symptoms in the study, as well as safety monitoring through Adverse Events (AE) reporting (see Human Subjects section), we believe this will provide a reasonable level of protection for a control group for this trial.

Experimental Treatments: Subjects will be randomized to (1) CPT or (2) IDC.

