Cognitive Processing Therapy (CPT): CPT is a manualized, 12-session 1:1 cognitive therapy that has been designed for patients with PTSD [76]. In this study the sessions will be conducted weekly. The stated goal of CPT is "to assist the client in refraining from assimilating (distorting the event to fit prior beliefs) and in accommodating schemas to the new information without over-accommodating".[77] CPT uses Socratic questioning targeting distorted cognitions such as self-blame, hindsight bias, and other guilt cognitions. CPT is focused on the cognitive components of the therapy without exposure. Therapy will be provided by psychologists who either have been or will be trained in conventional CPT through the VA rollout initiative. [[name] will be responsible for coordinating therapy and therapists will have weekly case consultation/supervision from a qualified CPT consultant ([name], who is a national CPT trainer and supervisor).]

Individual Drug Counseling (IDC): IDC will serve as the control group. The current standard of treatment for individuals entering buprenorphine maintenance is to do drug counseling. In most VA settings, including VA Connecticut Healthcare System, psychiatric symptoms (such as PTSD) are evaluated but psychiatric treatment is often deferred until the individual demonstrates a commitment to treatment and demonstrates abstinence. Standard counseling is the primary means to achieve these goals. IDC uses a semi-structured, time-limited addictions-counseling model in a 1:1 setting. The main focus is on helping individuals achieve and maintain abstinence by encouraging behavioral changes, such as avoiding triggers, structuring one's life, and engaging in healthy behaviors (e.g., exercise). The IDC manual provides an organized, concise version of what is currently practiced by most addiction counselors. In operationalizing this approach, the developers drew from their own clinical experience and that of expert drug counselors in the field. The approach is consistent with the 12-step approach that regards recovery as a gradual process, and participation in self-help groups such as Alcoholics Anonymous or Narcotics Anonymous is strongly encouraged. IDC will be conducted by study personnel and supervised by [name] on a weekly basis.[78]

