Subject Payment. All participants will be compensated for their participation. Participants will be paid \$30 for the initial screening/baseline assessment. They will be compensated \$30 for each medication visit (x7), and \$45 for follow up visits. There will be no payment for therapy sessions. Individuals can receive up to a total of \$330 if attending all scheduled treatment and visits. Payment will be made through electronic funds transfer (EFT). Participants will need to provide us with your banking information by completing a special payment form. Alternatively, if participants do not have a bank account, a check will be mailed to them instead. This check(s) will be mailed to the address they provide us with. Patients may choose to receive gift certificates issued to them for use at the VCS canteen (retail store) or VCS cafeteria here at the VACHS in lieu of EFT/check payment. If a patient chooses to receive payment by gift certificate they will be paid for the telemedicine/telehealth visits they participated in at their next in-person visit (e.g. if they complete weeks 2 and 3 by telephone they will receive gift certificates for weeks 2, 3, and 4 at the week 4 visit). Study payments are subject to withholding for outstanding federal debts (i.e., defaulted student loans, interstate child support, back taxes etc) without notification.

Power analysis: The sample size calculation for our primary hypothesis (change in PTSD symptoms) was based on findings from one of the largest and most comprehensive meta-analysis reports on PTSD treatment to date.[36] The report evaluated N=112 studies and reported on 137 comparisons, using validated PTSD symptom measures. The meta-analysis reported that the *effect sizes* for psychotherapy when contrasted with a control group were consistently large and averaged $g=1.14$. Three studies administered CPT specifically and the overall effect size for those was large and averaged $g=1.69$. For this study we conservatively are basing our calculations on a moderate effect size by Cohen's definition.[95] For the First and Second Primary aim we estimate that with 60 subjects randomized to each group we have 80% power to detect a medium effect size ($f=0.25$) at two-sided alpha level of 0.05, and assuming 25% dropout we will recruit a total of N=160.]

Data Analysis:

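### No eligibility rule covers trauma-focused therapy already under way at entry, so some IDC patients could be receiving CPT elsewhere and the CPT-IDC difference could be pulled toward zero

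*Combined protocol and SAP*

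**What the plan says.** Section 6 (Research Plan, Experimental subjects) names four recruitment sources, the first being patients "from the PTSD clinic patients at the local VAs". The Overview adds that "All subjects will be maintained on buprenorphine and the standard clinical treatment"; the content of that standard treatment is not defined.

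The inclusion criteria concern age, current PTSD on the CAPS-5, opioid use disorder, and pregnancy and contraception. The exclusion criteria run from pregnancy or lactation, through unstable medical illness, psychotic disorders and acute suicidal or homicidal risk, to the last item, "Those with known allergy or intolerance to buprenorphine". None refers to psychotherapy.

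Background treatment is dealt with in two other places. Under the inclusion criteria, "randomization will be stratified by presence of concurrent medications". Under Medication Compliance, "Other formal treatment concurrent with their study treatment (including self-help meetings) will be monitored". The Data Analysis section makes no use of the monitored information in the primary or secondary comparison; treatment utilization appears only as an exploratory follow-up outcome.

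Two passages show what the design expects of the control arm. The Potential Risks text says that PTSD symptoms are not addressed in IDC. The description of Phase III offers CPT after the study to those who did not have it during the study.

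**The concern.** The trial asks whether CPT reduces PTSD symptoms more than drug counseling does. That contrast requires IDC patients not to be getting CPT, or something close to it, from another clinic during the same 12 weeks. The Purpose and Background sections describe CPT as nationally disseminated and trauma-focused therapy as first-line under the guideline, so PTSD clinics are a natural place for it to be in progress. Followed exactly, the plan allows a patient in mid-course to be randomized to IDC.

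Such a patient brings the experimental therapy into the control arm. A patient in mid-course who is allocated to CPT may already have had part of the benefit before baseline. Both effects shrink the observed difference. The plan has little power to absorb this, and a null result would leave open whether CPT failed or the control arm was partly treated.

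**Working it through.** **Inputs from the plan.** The Power analysis gives effect size f = 0.25, two-sided alpha 0.05, stated power 80%, and the calculation is made "with 60 subjects randomized to each group". Data Analysis lowers the significance level to 0.025 for the two PTSD measures.

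**Input not in the plan.** Let c be the net share of IDC patients who obtain the full CPT benefit elsewhere. No figure for c is given, so 5% and 10% are used as assumptions.

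**Step 1: reproduce the plan.** For two equal groups d = 2f = 0.5. The noncentrality is d × √(n/2) = 0.5 × √30 = 2.739 on 118 degrees of freedom. Power is 77.5% by the noncentral t (78.2% by the normal approximation), slightly below the stated 80%. This two-group comparison is a simplification of the planned treatment-by-time test.

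**Step 2: dilution.** If a share c of the IDC arm gains the full effect d, the IDC mean moves by c × d, and the difference becomes d × (1 − c), with the standard deviation held at its planned value.

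| c (assumed) | effective d | noncentrality | power, alpha 0.05 | power, alpha 0.025 |
|---|---|---|---|---|
| 0 | 0.500 | 2.739 | 77.5% | 68.0% |
| 5% | 0.475 | 2.602 | 73.3% | 63.0% |
| 10% | 0.450 | 2.465 | 68.6% | 57.8% |

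**Step 3: partial benefit.** If 10% of IDC patients had outside therapy but gained only half the effect, then c = 0.10 × 0.5 = 0.05 and power is 73.3%, not 68.6%. The full-benefit row is therefore an upper bound on the loss for a given share.

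**Step 4: is there a usable rate?** The only related figure is in Preliminary studies, part (4): "Of those with PTSD, 10 (21.5%) were referred to trauma focused treatment" (10/46 is 21.7%). It counts referrals among new buprenorphine-clinic admissions over one year. It does not count therapy in progress at the time of entry, and it does not describe PTSD-clinic patients. Only 4 of the 46 (8.7%) were referred to CPT specifically. It does not estimate c.

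**The case against.** The case for leaving the plan alone has several parts.

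- **Usual care makes the overlap uncommon.** The IDC section says that "psychiatric treatment is often deferred until the individual demonstrates a commitment to treatment and demonstrates abstinence", and the Background says that specialty PTSD clinics often require sobriety first. This stands as a reason to expect a small share. It is a description of practice, though, not an entry rule, and it applies least to patients found in a PTSD clinic.
- **Allowing background care suits a real-world trial with a usual-care control.** This is a fair position on comorbidity and medication, which is what the plan's real-world rationale covers. The rationale does not extend to outside delivery of the therapy being tested.
- **Randomization balances prior therapy, and everyone must still meet current PTSD criteria.** Both points limit the effect: full responders are screened out, and a mid-course patient may have only part of the benefit still to come. Balance does not restore the contrast, because outside CPT replaces the missing treatment in IDC and largely duplicates it in the CPT arm.
- **The planned effect is conservative beside the cited meta-analytic values (g = 1.14, and 1.69 for CPT).** If effects that large held here, power would be ample. The plan itself argues that efficacy in comorbid patients cannot be assumed, and dilution shrinks the estimated difference whatever the power.
- **Outside treatment is already monitored.** This stands, and most of the recording is therefore in hand. What is missing is an entry rule and a stated use of the data.

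A reader might infer from the chart review that about one IDC patient in five will be in trauma-focused therapy, which would put power near 57%. The documents do not support that, for the reasons in Step 4 of the working. Nor do they show that CPT is routinely under way in these particular clinics; they describe a national rollout and a guideline recommendation.

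**Conclusion.** The gap holds: the plan recruits from PTSD clinics and neither excludes, stratifies on nor analyzes trauma-focused therapy in progress outside the study. The direction of the effect is toward no difference. Its size is unknown. On the assumption that a net 5% to 10% of IDC patients obtain the full benefit elsewhere, power falls by about 4 to 9 percentage points, from 77.5% to 73.3% or 68.6%, and each figure is the worst case for its share. The result rests on the plan's own d = 0.5, 60 analyzable patients per arm, two-sided alpha 0.05 and a two-group approximation. The documents do not show that contamination will be large; they show that the plan does not rule it out, and ruling it out at entry is inexpensive.

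**What to change.** 1. **Eligibility.** Add an exclusion, applied at screening only, for a course of CPT or other trauma-focused psychotherapy currently under way. Nothing is withheld from anyone who has been enrolled.
2. **Reporting.** Use the monitoring already described under Medication Compliance to record the type and start date of any outside trauma-focused therapy begun during the 12 weeks, and tabulate it by arm. Table 1 lists no form for this, so a short item at existing visits would be needed.
3. **Analysis.** Keep the intent-to-treat comparison primary. Any analysis that takes account of outside therapy should be prespecified and labeled supportive. It should not simply enter that therapy as a covariate or drop those patients: it starts after randomization, may depend on allocation and symptoms, and naive adjustment can bias the comparison. The question the analysis answers and its assumptions should be written down before the data are examined.

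The cost is one eligibility amendment, one short data item and a paragraph in the analysis section. The downside is a modest loss of eligible patients, limited if PTSD treatment is deferred as often in this population as the plan says. The exclusion deals only with therapy in progress at entry; therapy begun later is handled by items 2 and 3.

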Study data will be collected and managed using REDCap electronic data capture tools hosted at VA CT Healthcare System. REDCap (Research Electronic Data Capture) is a secure, web-based application designed to support data capture for research studies, providing 1) an intuitive interface for validated data entry; 2) audit trails for tracking data manipulation and export procedures; 3) automated export procedures for seamless data downloads to common statistical packages; and 4) procedures for importing data from external sources.

Descriptive statistics and graphs will be used to summarize the data on all randomized subjects. All continuous variables will be examined for adherence to the normal distribution using normal probability plots and Shapiro-Wilk tests. Transformations will be applied if needed. If normality is not satisfied and transformations do not help with achieving normality alternative analytic strategies will be considered such as generalized estimating equations (GEE) or nonparametric methods for repeated measures analysis. Baseline demographic and clinical characteristics for the two randomized groups (e.g., age, gender, severity of PTSD, and opiate use) will be compared using chi-square tests for categorical variables and t-tests or nonparametric tests for continuous variables. If there are baseline differences between study treatment groups, these variables will be used as covariates in the mixed-effects models analyses described below. Drop outs and completers will also be compared on baseline characteristics using the same approach. Between group differences in treatment retention, medication compliance and frequency of the occurrence of side effect symptoms across the treatment period will also be assessed. Residual plots and other diagnostics will be used to assess model assumptions.

The primary analyses will be intent-to-treat but sensitivity analyses on completers and non-completers will also be performed. All statistical testing will be at a two-tailed alpha level of 0.05. *Adjustments for multiple comparisons will be conducted among measures in specific domains. In the case of PTSD symptoms (use of 2 measures, PCL-5 and CAPS-5) and opiate use (use of TLFB and urine toxicology) the level of significance will be adjusted to 0.025.*

Primary and Secondary Hypotheses:

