For the primary and secondary hypotheses, we will use mixed effects models to assess changes in PTSD symptoms and opiate use over time. Treatments will be used as between-subject factors and time (in weeks) will be used as a within-subject factor. The primary outcome variables will be PTSD symptoms as measured by generated from the PCL-5 and CAPS scales. The secondary outcome variables will be frequency of opiate use generated from the TLFB and confirmed with urine toxicology results each medication visit (weeks 1-4, 6, 8, 12) and follow-up. The use of the mixed-effects models approach for the analysis of our longitudinal data has several specific advantages. Unlike traditional repeated measures analyses, mixed effects models allow for different numbers of observations per subject, use all available data on each subject and are unaffected by randomly missing data. They also provide flexibility in modeling the correlation structure of the data.[96]

Primary Aim 1. We hypothesize that CPT will significantly reduce PTSD symptoms compared to IDC in Veterans and civilians with PTSD and comorbid OUD maintained on buprenorphine.

This hypothesis will be tested by the interaction of treatment (CPT vs. IDC), and time in the mixed model specified above. Significantly greater decrease in PTSD symptoms in the CPT group will be considered supportive of the hypothesis.

Secondary Aim 1. We hypothesize that CPT will significantly reduce opioid use compared to IDC in Veterans and civilians with PTSD and comorbid OUD maintained on buprenorphine.

This hypothesis will be tested by the same approach as described in primary aim 1 but with frequency of opioid use as the dependent measure.

Exploratory Hypothesis:

We hypothesize that CPT will significantly improve retention (days in treatment) compared to IDC in Veterans and civilians with PTSD and comorbid OUD maintained on buprenorphine.

This hypothesis will be tested using ANOVA or nonparametric equivalent comparing the two treatment groups (CPT vs. IDC).

We hypothesize that CPT will significantly improve psychosocial functioning (measured by the VR-12 survey) compared to standard counseling in Veterans and civilians with PTSD and comorbid OUD maintained on buprenorphine.

This hypothesis will be tested by the interaction of treatment (CPT vs. IDC) and time.

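### Two sites enrol, but site is neither a named randomisation stratum nor a pre-specified model term; the likely loss is small and cheap to prevent

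*Combined protocol and SAP*

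**What the plan says.** All of this is in section 6 (Research Plan) of the combined protocol and SAP.

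- **Sites.** The Overview states that "The Bedford VAMC has been added as an additional enrollment site for this study". Under Experimental subjects, the 160 participants "will be enrolled at 2 sites (VA Connecticut Healthcare System, Bedford VAMC"). No enrolment target is given for either site.
- **Allocation.** The note after the inclusion criteria says that "randomization will be stratified by presence of concurrent medications". This is the only stratum named. The documents do not describe how the sequence is generated or whether each site has its own list.
- **Models.** Under Primary and Secondary Hypotheses: "Treatments will be used as between-subject factors and time (in weeks) will be used as a within-subject factor". For the primary aim, "This hypothesis will be tested by the interaction of treatment (CPT vs. IDC), and time in the mixed model specified above". The secondary aim uses the same approach, and no exploratory test adds a site term.
- **Covariates.** Data Analysis has a conditional rule: "If there are baseline differences between study treatment groups, these variables will be used as covariates in the mixed-effects models analyses described below". The examples given are age, gender, PTSD severity and opiate use.
- **Sample size.** The Power analysis says that "with 60 subjects randomized to each group we have 80% power" for f = 0.25 at two-sided 0.05, and inflates for 25% dropout to 160.

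**The concern.** In a psychotherapy trial, site can affect outcome through the therapists, the CAPS-5 evaluators, the patients who are referred and the care that surrounds the study. If site is in neither the allocation nor the analysis, two things can happen. By chance, the participants at one site may fall mostly in one arm, so that part of the difference between sites appears as a difference between CPT and IDC. And any variance due to site stays in the residual, which costs precision.

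The primary test limits which site differences matter. It is a treatment-by-time interaction, so a site whose participants score higher throughout largely cancels within participants. What remains is a site difference in *change* over time, for example because one team's therapy works faster. Below, D is that difference in SD units of change.

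**Working it through.** **Inputs from the protocol:** 160 recruited, 120 analysed (60 per arm), f = 0.25, which is d = 2f = 0.50 for two groups, and two-sided alpha 0.05.
**Assumptions:** Bedford's enrolment (20 to 40 of 160, with 80 as a contrast) and D (0.25 to 0.5 SD, with 0.8 as an extreme).

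**1. The plan's own figure.** Power = Φ(d√(n/2) − 1.96) = Φ(0.50 × √30 − 1.96) = Φ(0.779) = 78.2%, close to the stated 80%. Recruitment: 120 / 0.75 = 160, as stated.

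**2. Chance of a 2:1 or worse split at Bedford if allocation ignores site.** Let k be the smallest whole number that is at least two thirds of m, the number enrolled there. Independent allocation gives 2 × P(X ≥ k), X ~ Binomial(m, ½). Totals fixed at 80:80 give the same tail from the hypergeometric distribution (160, 80, m).

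| Bedford m | Split (k : m−k) | Independent | Totals fixed 80:80 |
|---|---|---|---|
| 20 | 14:6 | 11.5% | 9.2% |
| 30 | 20:10 | 9.9% | 6.7% |
| 40 | 27:13 | 3.8% | 1.7% |
| 80 | 54:26 | 0.2% | below 0.01% |

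**3. Shift in the contrast after a 2:1 split.** With 60 per arm, shift = D × (difference in Bedford counts between arms) / 60.

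- 12 analysed at Bedford (8:4), D = 0.5: 0.5 × 4/60 = 0.03 SD.
- 24 analysed at Bedford (16:8), D = 0.5: 0.5 × 8/60 = 0.07 SD.
- 24 analysed at Bedford, D = 0.8: 0.8 × 8/60 = 0.11 SD.

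If 20 or 40 are recruited and 25% are lost, 15 or 30 are analysed. At D = 0.5 the shifts are then 0.5 × 5/60 = 0.04 and 0.5 × 10/60 = 0.08 SD. All of these compare with a design effect of 0.50 SD.

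**4. Precision.** With share s at Bedford, leaving site out multiplies the residual variance by 1 + s(1−s)D².

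| Bedford of 160 | s(1−s) | D | Variance factor | Standard error |
|---|---|---|---|---|
| 20 | 0.109 | 0.25 | 1.007 | +0.3% |
| 20 | 0.109 | 0.50 | 1.027 | +1.4% |
| 40 | 0.188 | 0.25 | 1.012 | +0.6% |
| 40 | 0.188 | 0.50 | 1.047 | +2.3% |

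**5. Simulation** (120 participants, one change score each, 40,000 runs per setting). With site in neither the allocation nor the model, type I error was 4.8% to 5.1% for Bedford shares of 10% to 30% and D of 0.5 or 0.8. Power at d = 0.50 and D = 0.5 was:

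| Bedford share | Site ignored | Site as stratum and model term | Gain |
|---|---|---|---|
| 10% | 76.5% | 77.6% | 1.1 points |
| 20% | 76.0% | 77.4% | 1.4 points |
| 30% | 75.1% | 77.4% | 2.3 points |

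Stratifying by site without modelling it made the test conservative: type I error was 4.1% at a 20% share and D = 0.8.

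**The case against.** The strongest reply is that the protocol is silent on site lists, and silence does not show that allocation ignores site. Bedford has its own investigator, so a separate list is possible. Bedford may also be large enough for balance to look after itself. Several features would narrow site differences: manualised treatments, therapist certification, weekly supervision, fidelity rating, blinded evaluators, and therapy by video or telephone. The documents do not say that therapists or evaluators differ by site. The covariate rule gives its variables only as examples, so site is not excluded from it.

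Most of this stands as a limit on size. It does not answer the point about the analysis. The covariate rule acts only after baseline differences have been seen, so it does not replace a term fixed in advance. Separate lists, if they exist, would still leave site out of the models.

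Four stronger readings are tempting, and the documents do not support them:

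- *False-positive risk rises.* It does not; randomisation remains valid, and simulated type I error stays near 5%.
- *Bedford is a small site and likely to be badly split.* Its size is not given, and at 80 participants a 2:1 split is very unlikely.
- *Separate ethics oversight makes the problem worse.* It has no bearing on allocation or variance.
- *A within-site result would show that the effect is not one team's.* With 20 to 40 at Bedford, before dropout, the 95% interval for its own contrast is about ±1.96 × √(4/20) = ±0.88 SD to ±1.96 × √(4/40) = ±0.62 SD, too wide to show consistency.

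**Conclusion.** The point holds in a limited form. As written, the plan neither names site as a stratum nor pre-specifies it in any model, and it gives no reason. The consequence is a modest chance of a lopsided Bedford (about 12% to 4%, or 9% to 2% with fixed totals, for 20 to 40 participants). In that event the shift is a small fraction of the design effect. There is also a precision loss of 0.3% to 2.3% in the standard error for D of 0.25 to 0.5. All of these sizes rest on assumed values of Bedford's enrolment and D, and the split probabilities also assume that no site lists exist. The case for change is that the better method costs almost nothing and that 60 per arm, at 78.2% power, leaves no margin.

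**What to change.** - Before outcome data are reviewed, pre-specify site and site-by-time as fixed effects in the primary and secondary mixed models. The site-by-time term is the one that bears on the treatment-by-time test.
- Stratify any remaining allocation by site as well as concurrent medication. If separate site lists already exist, say so and describe them. The protocol describes REDCap for data capture and management only, so the system that issues allocations should be named.
- Report the CPT-IDC difference by site descriptively, with its interval, and claim nothing about consistency from it.

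The cost is four strata instead of two, one or two more model terms, and a short change of wording. The model terms remain worth adding even if enrolment is nearly complete.
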